4.6.2 Exclusion criteria

- Patients where the new breast cancer diagnosis is in the contralateral breast.
- For patients who present with new bilateral breast cancer, the side with no previous cancer will be excluded.

- Patients diagnosed with distant metastatic disease with no evidence of LRR.
- Patients diagnosed with angiosarcoma.
- Patients with previous history of non-breast cancer treatment that was non-curative in intent
- Patients who have had previous ipsilateral surgery for atypia, benign conditions, or phyllodes tumour and other breast sarcomas AND no previous ipsilateral primary breast cancer resection.
- Patients under 18 years old.
- Patients lacking capacity to provide written informed consent.

5. Data collection

The following dataset will be collected prospectively during the 24 months patient recruitment phase. Data regarding the management of LRR will be collected prospectively as the patient's care progresses.

- 1. Patient demographics (at the time of LRR diagnosis) collected will include;
 - 1.1 Centre name and ID
 - 1.2 Age (years)
 - 1.3 Current menopausal status (pre-menopausal, post-menopausal, perimenopausal)
 - 1.4 BMI
 - 1.5 Smoking status (non-smoker, ex-smoker, current smoker)
 - 1.6 Patient performance status (0 to 4; based on Eastern Cooperative Oncology Group score)
 - 1.7 Family history risk as defined by NICE guideline; CG164[65] (unknown / population risk / moderate risk / high risk / BRCA mutation positive / other known germline breast cancer susceptibility gene pathogenic mutation- e.g. TP53 gene mutation)

2. Treatment detail about the original breast cancer

Surgery

- 2.1 Date of original breast cancer surgery
- 2.2 Screening or symptomatic diagnosis
- 2.3 Age at original diagnosis

- 2.4 Type of breast surgery (none / breast conserving surgery / mastectomy + immediate breast reconstruction / mastectomy and delayed reconstruction/ mastectomy with no reconstruction)
- 2.5 If breast conserving surgery was performed for invasive lobular cancer, was MRI performed (Yes/No/Not applicable)
- 2.6 What was the original tumour location (upper inner quadrant / upper outer quadrant / lower inner quadrant / lower outer quadrant / subareolar or central)
- 2.7 Type of axillary surgery (none / sentinel lymph node biopsy / axillary node clearance / axillary node sampling / targeted axillary dissection)
- 2.8 If sentinel lymph node biopsy, method of localisation (dual technique with blue dye and radioisotope / radioisotope alone / blue dye alone / other methods)
- 2.9 Was the original breast cancer inflammatory breast cancer (Yes/No)

Pathology

- 2.10 Tumour subtype (invasive ductal / invasive lobular / mixed ductal and lobular / other subtypes / pure ductal carcinoma in situ)
- 2.11 Tumour grade (1 to 3 for invasive / low to high grade for ductal carcinoma in situ)
- 2.12 Tumour size (in mm; invasive tumour size, unless DCIS)
- 2.13 Multifocal or multicentric cancer (Yes/No)
- 2.14 Lymphovascular invasion (Yes/No)
- 2.15 Closest radial margin after final surgery (in mm)
- 2.16 Were anterior or posterior margins close (1mm or less)? If Yes, please state which (anterior / posterior / both) and distance in mm (0,1)
- 2.17 Number of positive axillary nodes (state macro- or micrometastasis)
- 2.18 Number of axillary lymph nodes retrieved
- 2.19 Oestrogen receptor Allred score (ER; 0 to 8; please state if any other scoring system was used and its score; e.g. H-score)
- 2.20 Progesterone receptor Allred score (PR; 0 to 8; please state if any other scoring system was used and its score; e.g. H-score)
- 2.21 HER2 receptor status (Positive or negative; please state immunohistochemistry score 0/1+/2+/3+; if 2+ was FISH test done? What was the final HER2 receptor status if FISH test done; positive/negative/not applicable)
- 2.22 Ki67 test? If Yes, please state %

Adjuvant treatment

- 2.23 Receipt of radiotherapy after breast conserving surgery or mastectomy (Yes/No/Not applicable)
- 2.24 If radiotherapy after breast conserving surgery, please state radiotherapy regimen (whole breast radiotherapy; 40 Gy in 15 fractions / whole breast radiotherapy; 27Gy in 5 fractions (hypofractionated) / partial breast radiotherapy / whole breast radiotherapy with boost)
- 2.25 Radiotherapy to the axilla (Yes/No)
- 2.26 Supraclavicular fossa radiotherapy (Yes/No)
- 2.27 Internal mammary node radiotherapy (Yes/No)
- 2.28 Receipt of adjuvant endocrine therapy (Yes/No)
- 2.29 If receiving or received endocrine therapy, please state duration received (total number of years)
- 2.30 Please state first line endocrine therapy (tamoxifen / letrozole / anastrozole / exemestane / ovarian suppression / others; please specify)
- 2.31 What was the duration of the first line endocrine therapy? Please state number of years
- 2.32 Please state second line endocrine therapy if applicable (not applicable/ tamoxifen / letrozole / anastrozole / exemestane/ ovarian suppression / others; please specify). Please state the duration in number of years (if applicable)
- 2.33 Receipt of chemotherapy (Yes/No)
- If received chemotherapy was is adjuvant or neoadjuvant? 2.34
- 2.35 Was an Oncotype Dx or other predictive test used? (Yes/No; If Yes, what test was used and please state the score)
- 2.36 Please select which chemotherapy agents the patient received (epirubicin / doxorubicin / docetaxel / paclitaxel / cyclophosphamide / carboplatin / capecitabine / others; please state)
- 2.37 Was chemotherapy stopped early (e.g. due to side effects); Yes/No
- 2.38 Receipt of anti-HER2 treatment (Yes/No). If Yes, was it trastuzumab (Herceptin) or trastuzumab (Herceptin) and pertuzumab (Perjeta)?
- 2.39 Receipt of bisphosphonates (Yes/No)
- 3. Treatment detail about locoregional recurrence

Diagnosis

- 3.1 Date of diagnosis for LRR
- 3.2 Screening or symptomatic diagnosis
- 3.3 Age at diagnosis of LRR
- 3.4 Tumour subtype (invasive ductal / invasive lobular / mixed ductal and lobular / other subtypes / pure ductal carcinoma in situ)
- 3.5 If invasive cancer diagnosis, was there associated ductal carcinoma in situ? (Yes/No)
- 3.6 Tumour grade (1 to 3 for invasive; low to high grade for ductal carcinoma in situ)
- 3.7 Oestrogen receptor Allred score (ER; 0 to 8; please state if any other scoring system was used and its score; e.g. H-score)
- 3.8 Progesterone receptor Allred score (PR; 0 to 8; please state if any other scoring system was used and its score; e.g. H-score)
- 3.9 HER2 receptor status (Positive or negative; please state immunohistochemistry score 0/1+/2+/3+; if 2+ was FISH test done? What was the final HER2 receptor status if FISH test done; positive/negative/not applicable)
- 3.10 Ki67 test? If Yes, please state %
- 3.11 If patient had breast conserving surgery for the original cancer, please state the tumour location for the recurrent cancer (upper inner quadrant, upper outer quadrant, lower outer quadrant, lower inner quadrant, subareolar or central)

Investigations

- 3.12 Please state the site(s) of LRR (breast / skin / chest wall / axilla / internal mammary nodes / supraclavicular nodes / infraclavicular nodes; please select all that applies)
- 3.13 If breast LRR, what was the maximal tumour size on imaging (in mm)
- 3.14 Was axilla ultrasound scan performed (Yes/No)
- 3.15 Was it reported as normal (Yes/No)
- 3.16 If reported as abnormal, what was the FNA/core biopsy result (C1 to 5 or B1 to 5)
- 3.17 Was staging investigation performed to investigate for the presence of distant metastasis (Yes/No)
- 3.18 If staging was performed, what modality was used? Please select from the following options (CT chest/abdomen/pelvis / CT chest/abdomen/pelvis and bone scan / PET CT / Others)

- 3.19 Did staging investigations reveal any evidence of distant metastasis (Yes/No; if No skip to section to 3.23)
- 3.20 If evidence of distant metastasis, please state site (bone / brain / liver / lung / other sites; please select all that applies)
- 3.21 Did the patient undergo surgery in the presence distant metastasis (Yes/No; If no please skip to section 3.39)
- 3.22 Was any neoadjuvant systemic therapy used for patients with LRR (neoadjuvant chemotherapy / neoadjuvant endocrine therapy / CDK inhibitors / others; please state rationale for neoadjuvant systemic therapy; i.e. curative intent or palliative with downstaging to enable surgery for local control)

Surgery

- 3.23 Did the patient receive surgery for LRR (Yes/No; if No please skip to section 3.39)
- 3.24 If the patient did not receive surgery for LRR, please state the reason (LRR unresectable / patient deemed unfit for surgery / patient choice / due to distant metastasis identified on staging scans / commenced on systemic therapy first / other reasons; please specify)
- 3.25 State the date of surgery for LRR
- 3.26 What breast surgery was performed (none / simple mastectomy / mastectomy with immediate breast reconstruction (implant or fully autologous or autologous with implant) / mastectomy with deconstruction (taking down of previous reconstruction) / repeat breast conserving surgery / wide local excision of skin flap or chest wall recurrence (please state the method of wound closure; direct closure / skin graft / flap closure)
- 3.27 What axillary surgery was planned (none / sentinel lymph node biopsy (no previous axillary surgery) / repeat sentinel lymph node biopsy / axillary node sampling / axillary node clearance / targeted axillary dissection / axillary exploration after previous axillary node clearance / others)
- 3.28 If repeat sentinel lymph node biopsy was performed, what localisation method was utilised (dual technique with blue dye and radioisotope / radioisotope only / blue dye only / others)
- 3.29 If repeat sentinel lymph node biopsy was performed, was it successful in identifying the sentinel lymph node (i.e. was a 'hot' and/or blue lymph node identified?; Yes/No)

3.30 If unsuccessful and no sentinel lymph node was identified during surgery, how did you proceed (no further axillary dissection / axillary node sampling / axillary node clearance)

LRR pathology

- 3.31 Multifocal or multicentric cancer (Yes/No)
- 3.32 Lymphovascular invasion (Yes/No)
- 3.33 Tumour size (invasive size in mm, unless DCIS)
- 3.34 Closest radial margin (in mm)
- 3.35 Were anterior or posterior margins close (1mm or less)? If Yes, please state which (anterior / posterior / both) and distance in mm (0,1)
- 3.36 Number of positive axillary nodes (state macro- or micrometastasis)
- 3.37 Number of lymph nodes retrieved

Adjuvant treatment for LRR (including further surgery)

- 3.38 Was further surgery to the breast required (Yes/No). If Yes, please state the type of further breast surgery (re-excision of margins / mastectomy)
- 3.39 Was further surgery to the axilla required (Yes/No). If Yes, please state the type of further axillary surgery and date (axillary node clearance / sentinel lymph node biopsy/ axillary node sampling)
- 3.40 Receipt of breast radiotherapy (Yes / No/ not applicable)
- 3.41 If radiotherapy after breast conserving surgery, please state radiotherapy regimen (whole breast radiotherapy; 40 Gy in 15 fractions / whole breast radiotherapy; 27Gy in 5 fractions (hypofractionated) / partial breast radiotherapy / whole breast radiotherapy with boost)
- 3.42 Post-mastectomy radiotherapy (Yes/No/ not applicable)
- 3.43 Radiotherapy to the axilla (Yes/No)
- 3.44 Supraclavicular fossa radiotherapy (Yes/No)
- 3.45 Internal mammary node radiotherapy (Yes/No)
- 3.46 Receipt of endocrine therapy (Yes/No)
- 3.47 If receiving endocrine therapy, please state the duration recommended at the MDT meeting (number of years)
- 3.48 What endocrine therapy was the patient prescribed (tamoxifen / letrozole / anastrozole / exemestane/ ovarian suppression / others; please specify)

- 3.49 Receipt of chemotherapy (Yes/No)
- 3.50 Please select which chemotherapy agents the patient received (epirubicin / doxorubicin / docetaxel / paclitaxel / cyclophosphamide / carboplatin / capecitabine / others; please state)
- 3.51 Receipt of anti-HER2 treatment (Yes/No). If Yes, was it trastuzumab (Herceptin) or trastuzumab (Herceptin) and pertuzumab (Perjeta)?
- 3.52 Receipt of other targeted treatment (Yes/No; if Yes, please specify)

6. Data validation and quality assurance

Data collected on each patient must be recorded by the Principal Investigator, or his/her designee, as accurately and completely as possible. The Principal Investigator is responsible for the timing, completeness, legibility, accuracy and signing of the data entry on REDCap database and the CRF. The Clinical Investigators must allow study staff access to any required background pseudonymised data from hospital records (source data e.g. medical records) on request.

All fields MUST be completed. All data submitted must be verifiable in the source documentation. These may include, but are not limited to, hospital records (from which medical history and previous and concurrent medication may be summarised into the REDCap database and the CRF), clinical and office charts, laboratory and pharmacy records, diaries, radiographs and correspondence. All documents will be stored in confidential conditions. Any deviation from this must be explained appropriately.

For quality assurance purposes, the Consultant principal investigator at all participating sites will be asked to identify an independent person to validate a proportion of the submitted data. Overall, approximately 5% of the dataset selected at random will be independently validated. If concordance between the number of cases submitted on REDcap and those identified independently is <90%, the Unit's data will be excluded from the analysis. This is consistent with the quality assurance procedure used in other large collaborative audit projects[66].

7. Data management and storage

Data collection will occur in accordance with GCP, Caldicott principles and the General Data Protection Regulation (GDPR) 2018, and will work in line with NHS confidentiality guidelines and codes of conduct. Data for each patient will be pseudonymised using a unique

alphanumeric study identification number. No patient identifiable data will be recorded into the REDCap database and the CRF for the purpose of the study.

Study data will be collected and managed using REDCap electronic data capture tools hosted at University of Manchester and made freely available to research collaboratives in the UK. REDCap (Research Electronic Data Capture) is a secure, web-based application designed to support data capture for research studies, providing 1) an intuitive interface for validated data entry; 2) audit trails for tracking data manipulation and export procedures; 3) automated export procedures for seamless data downloads to common statistical packages; and 4) procedures for importing data from external sources. More information about the consortium and system security can be found at http://www.projectredcap.org/.

The local PI will keep a secure record of the RedCap ID with corresponding NHS number (in England Wales), Community Health Index number (in Scotland), or Health and Care number (in Northern Ireland). This is required for the research team at each participating centres (Consultant PI, research nurse, and clinical trial assistants) to access the hospital electronic system at 3 and 5 years after LRR diagnosis to record the oncological outcome as specified in section 4.4.

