1.2.2 The role of radiotherapy in reducing locoregional recurrence rate

Radiotherapy is a key adjuvant treatment that reduces the risk of local recurrence[19] after BCS. The Early Breast Cancer Trialists' Collaborative Group (EBCTCG) meta-analysis has demonstrated that WBRT after BCS halves the rate at which recurrences (combined analysis of locoregional and distant metastasis) occur and reduces breast cancer death rate by about a sixth in the long term[19]. Additional studies have demonstrated that the addition of a radiotherapy boost to the tumour bed results in a further reduction in the local recurrence rate for young patients with high grade invasive cancer[20]. Partial breast radiotherapy is non-inferior to WBRT in older patients with early breast cancer in terms of achieving local control[21]. The PRIME II trial concluded that omission of WBRT may be considered for older patients (over 65 years old) with low risk, oestrogen receptor (ER) positive breast cancer after BCS given the modest effect of WBRT in reducing local recurrence risk in this patient group[22]. Therefore, whether patients go on to receive radiotherapy after BCS, as well as the type and regimen, may be individualised according to both patient and tumour factors.

Radiotherapy is also beneficial in patients with high recurrence risk (T3-4, N1-3) disease who undergo mastectomy. Radiotherapy to the chest wall +/- supraclavicular fossa has been shown to reduce LRR and breast cancer mortality even in patients with modest axillary lymph node burden (i.e. one to three nodes) who had received additional systemic therapy[23].

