4.6 Patient inclusion and exclusion criteria

4.6.1 Inclusion criteria

- Female or male patients more than 18 years old. Treated for previous unilateral or bilateral breast cancer (invasive cancer including all histological subtypes as well as ductal carcinoma in situ) with curative intent.
- No previous evidence of distant metastatic disease.
- Recently (within the last 6 months) diagnosed with new ipsilateral breast cancer locoregional recurrence (biopsy proven invasive cancer including all histological subtypes or ductal carcinoma in situ) +/- distant metastasis.
- Able to provide written informed consent.
- A *minimum of 3 months interval* between the resection surgery for the original cancer and the diagnosis of locoregional recurrence. There will be *no maximum interval time period*.

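### The radiotherapy regimen items (2.24 and 3.41) mix schedule with volume and boost and have no 'other' or 'unknown', so some courses after breast conserving surgery have no correct or no unambiguous answer

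*Protocol*

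**What the plan says.** In Protocol section 5, item 2.24 (original cancer) and item 3.41 (recurrence) share a stem and a first option: "If radiotherapy after breast conserving surgery, please state radiotherapy regimen (whole breast radiotherapy; 40 Gy in 15 fractions". The list then runs "whole breast radiotherapy; 27Gy in 5 fractions (hypofractionated) / partial breast radiotherapy / whole breast radiotherapy with boost" and closes. Neither item says whether more than one option may be chosen.

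Receipt of radiotherapy is asked separately. For the original cancer, item 2.23 reads "Receipt of radiotherapy after breast conserving surgery or mastectomy (Yes/No/Not applicable". For the recurrence, item 3.40 reads "Receipt of breast radiotherapy (Yes / No/ not applicable" and item 3.42 reads "Post-mastectomy radiotherapy (Yes/No/ not applicable". Nodal fields (2.25 to 2.27 and 3.43 to 3.45) are Yes/No.

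Three other statements bear on how these items will be answered. Section 4.6.1 sets "no maximum interval time period" between the original surgery and the recurrence. Section 6 says "All fields MUST be completed". Section 1.2.2 accepts that whether radiotherapy is given after breast conserving surgery, "as well as the type and regimen, may be individualised according to both patient and tumour factors".

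**The concern.** A closed list works only if every real case fits exactly one option. This one puts two different attributes in one field: the schedule (dose and fractions) and the volume or boost. Boost is elsewhere treated as something added to whole-breast treatment, both in section 1.2.2 and in Scenario 3 of the practice questionnaire. In the list it stands as an alternative to a schedule.

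The list also assumes that the two schedules shown are the only whole-breast schedules a site will meet. For item 2.24 that is hard to square with an eligibility rule that admits original treatment from any year.

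At stake is the regimen variable itself. Section 2.3 sets out to describe the radiotherapy used for recurrence and to investigate risk factors that include management of the primary cancer. Section 4.3 sets out to examine the treatment given for the initial cancer. If unlisted courses are placed under the nearest option, or boosted courses are coded differently from site to site, tabulations of regimen will contain errors that cannot be detected at analysis.

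**Working it through.** The plan gives no figure on this point, so the check is a count of the options followed by a test of each type of course against them.

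**Options in each of 2.24 and 3.41**
- Number of options: 4.
- Options that state dose and fractions: 2 (40 Gy in 15; 27 Gy in 5).
- Options that state volume or boost without a schedule: 2 (partial breast; whole breast with boost).
- Options for 'other' or 'unknown': 0.

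**Comparison with other items in section 5.** An 'other' option appears in 2.8, 2.30, 2.36, 3.18, 3.27, 3.28, 3.48 and 3.50, and item 1.7 has 'unknown'. Multiple selection is invited in 3.12 and 3.20 but not in 2.24 or 3.41, so single choice is implied without being stated.

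**Each type of course against the list**

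| Course | Options that fit | What is recorded |
|---|---|---|
| After breast conserving surgery: whole breast, listed schedule, no boost | 1 | Correct, with schedule |
| After breast conserving surgery: whole breast, listed schedule, with boost | 2 | Single choice loses either the schedule or the boost; multiple choice would keep both |
| After breast conserving surgery: whole breast, unlisted schedule, no boost | 0 | No correct entry |
| After breast conserving surgery: whole breast, unlisted schedule, with boost | 1 | Boost correct, schedule lost |
| After breast conserving surgery: whole breast, no boost, schedule not traceable | 0 determinable | No way to say so |
| After breast conserving surgery: partial breast | 1 | Type correct, no schedule |
| After mastectomy or chest wall excision | Regimen not asked | At most, receipt |

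The third and fifth rows fail whether the field is single or multiple choice. The second fails only under single choice.

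**Which item is exposed to what.** The absence of a maximum interval concerns the original treatment, so it bears on 2.24. Item 3.41 concerns current treatment. There the reason to expect courses outside the list is the protocol's own statement in section 1.2.2 that regimens are individualised. The overlap between schedule and boost applies to both items.

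**What the primary analysis needs.** Section 2.4.1 groups patients as breast conserving surgery with radiotherapy or mastectomy. That takes surgery type (item 2.4) and receipt of radiotherapy (item 2.23), both recorded for both groups. The adjustment covariates in section 8 are tumour and nodal staging, receptor profile and grade. The target is 2 × 165 = 330. None of these uses dose or fractionation.

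**The case against.** The strongest reply is that no planned analysis uses dose. The objectives ask about use of radiotherapy, section 4.3 asks about receipt of and compliance with recommended treatment, and section 1.5.1 speaks of an irradiated breast, which item 2.23 identifies. Boosted and partial-breast courses can be classified correctly by type and lack only detail. All of this stands, and it keeps the point small. It does not rescue the unboosted whole-breast course on an unlisted schedule, for which no listed answer is true. Having chosen to collect regimen, the study should be able to collect it correctly.

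A second reply is that section 6 does not make sites enter something untrue. It also requires data to be verifiable in source, and it closes by asking for deviations to be explained. That is fair. A reader might infer that the form compels false entries, but the text does not go that far. It leaves the site with two rules that the listed options cannot both satisfy, and an explanation outside the field gives no code to analyse.

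A third reply is that recording post-mastectomy and nodal radiotherapy as received or not is a proportionate choice in an observational dataset. This also stands. The absence of dose there is a matter of granularity.

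A reader might also infer that the main comparison is compromised, because radiotherapy is part of how its groups are defined. The documents do not support this: the grouping depends on receipt, and receipt is recorded.

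**Conclusion.** The point holds as a data-capture flaw limited to items 2.24 and 3.41. An unboosted whole-breast course after breast conserving surgery on an unlisted schedule has no correct option. A boosted course either fits two options or loses its schedule. Unboosted whole-breast courses on the two listed schedules are recorded correctly.

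The consequences are confined to describing radiotherapy for recurrence and evaluating the original treatment. The primary grouping, the disease-free survival analysis and the 330-patient target are unaffected.

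The number of patients affected cannot be worked out from the protocol, which gives no frequency for boost, partial-breast or other schedules. A reader might try to size it by counting the 40% assumed to have had mastectomy (section 8) as lacking a regimen. That would be wrong, because it includes patients who were never irradiated and so have no regimen to record.

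The ambiguity for boosted courses on a listed schedule assumes that the field takes a single answer, which is implied but not stated. The lack of an option for unlisted or untraceable schedules does not depend on that assumption. This is a cheap improvement and not a threat to the study's conclusions.

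**What to change.** In items 2.24 and 3.41:
- add 'other, please specify' and 'unknown';
- record boost as its own Yes/No field alongside the schedule, so that it no longer replaces it;
- ask sites to check these fields for patients already entered.

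Optionally, ask the same regimen item for radiotherapy after mastectomy or chest wall excision. This would add detail and is not needed to correct the flaw.

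The aim is to record what was given; no schedule is preferred.

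The cost is a small edit to REDCap and the case report form, plus some re-checking of records across the participating units (at least 50). Section 4.2.2 does not name radiotherapy prescription records among the sources reviewed, so for some older treatments the schedule may not be found and 'unknown' will be the honest entry.

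### The skip targets at items 3.19, 3.21 and 3.23 contradict the items they bypass, so the neoadjuvant question and the reason-for-no-surgery question miss the patients they address

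*Protocol*

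**What the plan says.** All the items are in Protocol section 5 (Data collection), part 3, on the locoregional recurrence (LRR).

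- Item 3.19: "Did staging investigations reveal any evidence of distant metastasis (Yes/No; if No skip to section to 3.23".
- Item 3.21: "Did the patient undergo surgery in the presence distant metastasis (Yes/No; If no please skip to section 3.39".
- Item 3.22: "Was any neoadjuvant systemic therapy used for patients with LRR". It also asks for the rationale: "i.e. curative intent or palliative with downstaging to enable surgery for local control".
- Item 3.23: "Did the patient receive surgery for LRR (Yes/No; if No please skip to section 3.39".
- Item 3.24: "If the patient did not receive surgery for LRR, please state the reason". Its answer options include "due to distant metastasis identified on staging scans / commenced on systemic therapy first".

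The shared jump target, 3.39, asks whether further axillary surgery was needed. Items 3.46 to 3.52 record receipt of endocrine, chemotherapy, anti-HER2 and other targeted treatment under a heading on adjuvant treatment. Section 6 adds a general rule that every field must be filled in.

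The primary endpoint (section 2.4.1) is DFS after LRR resection in patients presenting without distant metastasis. Section 8 restricts the DFS analysis to non-metastatic patients who go on to resection.

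**The concern.** Two items sit inside blocks that the skip rules tell the relevant patients to leave.

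Item 3.22 is worded for LRR patients in general and offers curative intent as a rationale, so it was not meant only for metastatic patients. Yet a No at 3.19 jumps over it. Item 3.24 is addressed only to patients without surgery, yet it follows directly after the rule that sends those patients to 3.39.

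Three things are at stake. First, pathological size and node count at LRR (3.33, 3.36) are natural prognostic factors. Without neoadjuvant status, tumours treated before surgery cannot be cleanly separated from untreated ones. Second, the DFS set is selected by resection, and 3.24 is the only item that explains why a non-metastatic patient falls outside it. Third, section 2.3 sets out to describe surgical and systemic management of LRR, and both items belong to that description.

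**Working it through.** The plan gives no figure to reproduce. The check is a trace of the three skip rules as written.

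**Inputs (section 5).** A No at 3.19 goes to 3.23. A No at 3.21 goes to 3.39. A No at 3.23 goes to 3.39. Otherwise the next item in sequence is answered.

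| Patient | Route | 3.22 reached? | 3.24 reached? |
|---|---|---|---|
| No metastasis, operated | 3.19 → 3.23 → 3.24 → 3.25 … | No | Yes, but it does not apply |
| No metastasis, not operated | 3.19 → 3.23 → 3.39 | No | No |
| Metastasis, operated | 3.19 → 3.20 → 3.21 → 3.22 → 3.23 → 3.24 … | Yes | Yes, but it does not apply |
| Metastasis, not operated | 3.19 → 3.20 → 3.21 → 3.39 | No | No |

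On consistent answers, 3.22 is reached only by operated metastatic patients. Item 3.24 is reached only by operated patients, and by none of those it is meant for. A non-metastatic patient started on systemic therapy with surgery still pending misses both.

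**Do the items themselves show that this was unintended?** They do. The first answer option quoted from 3.24, metastasis on staging, describes patients already sent away at 3.21. The second, systemic therapy first, describes patients sent away at 3.21 or 3.23. The landing item, 3.39, asks unoperated patients about further axillary surgery. All of this points to misnumbered targets.

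**Does another item recover the information?**
- Timing: for the original cancer, 2.34 asks whether chemotherapy was adjuvant or neoadjuvant. For the LRR, 3.49 asks only about receipt. No LRR item other than 3.22 gives timing or rationale.
- Reason for no surgery: no other item asks for it.
- The rule in section 6 that all fields be completed conflicts with the skips but does not say which prevails. Units could follow either.

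**Size.** For 3.22, every patient answering No at 3.19 bypasses it. As an illustration, the pilot audit in section 1.1 found 137 patients with LRR only and 114 with distant disease as well:

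- 137 / (137 + 114) = 137 / 251 = 0.546
- 0.546 × 500 = about 273 patients

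This counts non-metastatic patients, operated or not, who would bypass 3.22. It does not count patients who had neoadjuvant therapy; the protocol gives no rate for that. For 3.24, every unoperated patient bypasses it; the protocol gives no expected number.

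**Limit of the trace.** Item 3.17 ("Was staging investigation performed to investigate for the presence of distant metastasis (Yes/No") has no skip rule. An unstaged patient whose 3.19 is left blank has no defined route, so the result for 3.22 is exact only where 3.19 is answered No. The result for 3.24 does not depend on this, because a No at 3.23 bypasses it whatever came before.

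**The case against.** The strongest reply accepts the routing but disputes the consequences. Most of it stands.

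- **Recoverability.** A reader might infer that the data are lost for good. The documents do not support that. Section 4.2.2 makes the hospital records the data source, and section 7 has each principal investigator keep the link needed to return to them at 3 and 5 years.
- **Surviving information.** A reader might infer that pre-treated tumours could not be recognised at all. In fact imaging size for breast recurrences (3.13), axillary ultrasound and biopsy (3.14 to 3.16) and diagnostic grade and receptors (3.6 to 3.9) are kept. So are the dates of diagnosis and surgery (3.1, 3.25) and receipt of each drug class (3.46 to 3.52). These are partial evidence and do not replace 3.22.
- **Primary comparison.** A reader might infer that the primary analysis is undermined. It is not. The exposure is the surgery for the original cancer. The covariates named in section 8 are staging, receptor profile and grade, which section 1.2 treats as features of the primary tumour. Entry to the DFS set is fixed by metastasis and resection status, both of which are collected. The reason for no surgery describes selection; it does not determine it.
- **Unoperated metastatic patients.** Neoadjuvant therapy precedes surgery, so 3.22 hardly applies to them, and their bypassing it is of little consequence.
- **The live form.** Section 5 is a dataset list; the built REDCap form is not shown. Item 3.24 carries its own condition, and section 6 demands complete fields, so sites may be answering both items.

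What does not stand is any suggestion that the text is harmless. The listed targets contradict the items, nothing else in the LRR dataset captures either fact directly, and the section 6 rule does not resolve the conflict.

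**Conclusion.** The point holds as a contradiction within section 5. Followed as written, the form does not capture neoadjuvant status or rationale in the resected, non-metastatic population of the primary endpoint, and it captures no reasons for non-resection.

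The effect is on three secondary uses: prognostic modelling with LRR pathological size and nodes, the description of who enters the DFS set, and the management objective. The primary comparison by original surgery remains valid. No bias in any estimate has been shown, because the protocol gives no rate of neoadjuvant use.

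The conclusion assumes that 3.19 is answered No for patients without metastasis and that the built form uses the printed targets. The figure of about 273 of 500 also assumes the pilot audit's split. If the live form branches differently, only the protocol text is wrong.

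**What to change.** 1. Send a No at 3.19 to 3.22.
2. Route a No at 3.21 so that 3.24 is reached, either directly or through 3.23.
3. Send a No at 3.23 to 3.24, and from there to 3.40, because 3.39 concerns further axillary surgery.
4. Compare the live REDCap branching with the corrected text. Only if it has the same error, issue one query to back-fill 3.22 and 3.24 from the notes for patients already entered.

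With these targets, non-metastatic patients reach 3.22 whether or not they were operated on, and all unoperated patients reach 3.24.

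The cost is a correction to the protocol and CRF page and, if needed, a branching edit and a one-off back-fill of two items. Whether neoadjuvant therapy is used as a covariate when LRR pathology is modelled is optional and can be left to the SAP.
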